7.2. Number of Subjects

Approximately 59 subjects (assuming a 10% early drop-out rate) will be enrolled to obtain approximately 54 evaluable subjects in the final statistical analysis:

- Approximately 43 evaluable subjects with WT EZH2 (primary study population) and
- Approximately 11 evaluable subjects with MT EZH2

7.3. Treatment Assignment

Tazemetostat 800 mg twice daily will be administered starting on Cycle 1 Day 1 (C1D1). Tazemetostat is supplied by Epizyme in pre-counted, appropriately labeled bottles. Tazemetostat will be administered from C1D1 to the end of Cycle 24, for 24 months of therapy or until disease progression, unacceptable toxicity, or withdrawal of consent.

Rituximab will be administered by either subcutaneous injection or IV infusion according to the regional product prescribing information, labeling, and institutional guidelines. For subjects receiving rituximab via IV infusion, rituximab will be administered at a dose of 375 mg/m² on Day 1, 8, 15, and 22 of Cycle 1, and then on Day 1 of Cycles 3 through 6, accounting for an additional 4 doses (ie, a total of 8 doses of rituximab in 6 cycles).

For subjects receiving rituximab subcutaneously, rituximab will be administered at a dose of 375 mg/m² via IV infusion on Cycle 1 Day 1. Subcutaneous rituximab hyaluronidase will be administered as 1,400 mg rituximab and 23,400 Units hyaluronidase per 11.7 ml total volume (120 mg/2,000 Units per mL) on Cycle 1 Days 8, 15, and 22 and Day 1 of Cycles 3 through 6,

for a total of 8 doses of rituximab in 6 cycles (7 doses of SC rituximab after the initial IV infusion). Rituximab will be procured by the clinical sites from commercial sources.

7.4. Dose Adjustment Criteria

7.4.1. Dose Adjustment for Tazemetostat

Tazemetostat dose reductions and interruptions will be allowed; however, an interruption in the administration of tazemetostat for more than 14 days must be discussed with the Medical Monitor before treatment can be resumed.

Toxicity will be managed by concomitant medication (as appropriate), treatment interruption, dose reduction, and treatment discontinuation, or a combination of these. During treatment with tazemetostat, dose interruption and reduction for subjects who experience tazemetostat-**related** toxicity will be in accordance with the Dose Modifications instructions in Table 1.

For subjects who require dose interruption due to tazemetostat-related toxicity, the treatment may restart once the toxicity has been resolved to Grade ≤ 1 or baseline, unless otherwise noted, according to the Dose Modifications instructions in Table 1. No tazemetostat dose re-escalation is permitted.

For continuation of treatment for Cycle 2 and beyond, subjects must meet the following retreatment criteria:

- Platelet count must be $> 50 \times 10^9/L$
- Absolute neutrophil count (ANC) must be $\geq 0.75 \times 10^9 / L$, and
- Any Grade 3 or higher toxicity must have resolved to ≤Grade 1 or baseline, unless otherwise noted

Table 1: Dose Modifications for Tazemetostat Treatment-Related Toxicities

Tazemetostat-Related Toxicity ^a	During Therapy	Approximate Dose Adjustmentb			
	Grade 1				
All occurrences	All occurrences Continue tazemetostat				
	Grade 2 ^{c,d}				
1st occurrence		Maintain dose level			
2 nd occurrence (same or new toxicity)	Interrupt tazemetostat until	Restart at 600 mg BID			
3 rd occurrence (same or new toxicity)	resolved to Grade ≤ 1 or baseline ^b	Restart at 400 mg BID			
4 th occurrence (same or new toxicity)		Discuss with Medical Monitor			
Grade 3 ^c (Not Including Neutropenia and Thrombocytopenia)					
1 st occurrence		Restart at 600 mg BID			

Tazemetostat-Related Toxicity ^a	During Therapy	Approximate Dose Adjustmentb						
2 nd occurrence (same or new toxicity)	$\begin{array}{c} \text{Interrupt tazemetostat until} \\ \text{resolved to Grade} \leq 1 \text{ or baseline}^b \end{array}$	Restart at 400 mg BID						
3rd occurrence (same or new toxicity)	Discontinue tazemetostat	Not applicable						
Grad	Grade 3 Neutropenia (ANC: < 1.0 – 0.5 × 10 ⁹ /L) ^e							
ANC $\ge 0.75 \times 10^9 / L$	Continue tazemetostat	Maintain dose level						
$ANC < 0.75 \times 10^9/L$ 1 st occurrence	Interrupt tazemetostat until	Restart at 600 mg BID						
2 nd occurrence	resolved to ANC $\geq 0.75 \times 10^9/L$	Restart at 400 mg BID						
3 rd occurrence	Discontinue tazemetostat	Not applicable						
	Grade 3 Thrombocytopenia ^f							
1st occurrence	Interrupt tazemetostat until	Restart at 600 mg BID						
2nd occurrence	resolved to Grade ≤ 2 or baseline ^b	Restart at 400 mg BID						
3rd occurrence	Discontinue tazemetostat	Not applicable						
Grade 4								
Any occurrence	Interrupt tazemetostat until resolved to Grade 2 or less	Discuss with Medical Monitor						

ANC = absolute neutrophil count, ASCO = American Society of Clinical Oncology; BID = twice daily

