Section 5 (Introduction)	Updated existing information on the indication and study rationale.	To provide more comprehensive and up-to-date information.
	Added additional information on the investigational products.	To provide information on each of the investigational products.
Section 5.2.2 (Tazemetostat Clinical Experience) Section 12.2.2 (AESIs) Section 12.2.4 (Other Risks) Section 12.4 (Reporting of Adverse Events)	Updated based on the latest version of the tazemetostat IB and remove repetition in Section 12.2.4 (Other Risks)	To align with the current tazemetostat IB, version 11.0.
Section 7.4 (Dose Adjustment Criteria)	Updated the dose modification for tazemetostat	To align with the inclusion criteria and retreatment
Section 7.7 (Schedule of Procedures/ Assessments) Section 7.7 (Schedule of Procedures/ Assessments) Section 12.1.6 (Laboratory Assessments) Section 12.1.8 (Peripheral Blood Smear and Bone	Updated the dose modifications for rituximab. Included rows and footnotes to clarify which visits will be on site versus phone calls. Update to include informed consent, include/exclusion criteria, demographics and medical history, prior and concomitant medications, pregnancy testing, height and weight measurements, viral serology/virology, serum chemistries & coagulation, urinalysis, bone marrow aspirates, scans, ect. Clarified information on adverse events (AEs) and concomitant medications/ procedure. Added End-of-Treatment and Safety Follow-up visits. Added peripheral blood smears to test for abnormal morphology.	For clarity Updated to clarify the order of assessments and procedures Added as a safety assessment to align with prior safety commitments.
Marrow Aspirate/Biopsy) Section 8.2 (Subject Withdrawal Criteria)	Added additional information regarding subject withdrawal.	Add for clarity and alignment across tazemetostat protocols
Section 9.1 (Description of Study Drug)	Added tazemetostat FDA-approval information and updated the chemical name, structural formula of tazemetostat.	To provide more comprehensive and up-to-date information.
Section 9.2 (Concomitant Medication)	Updated to include additional information and guidance.	To provide more comprehensive and up-to-date information as well as for alignment across tazemetostat protocols.

Section # and Name	Description of Substantial Change	Rationale

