7.5. Continuation of Treatment

Subjects will receive study treatment for 24 cycles across the clinical trial or until disease progression, unacceptable toxicity, or withdrawal of consent. However, if subjects experience disease progression during study treatment, they may be permitted to continue treatment on study

^a Excluding alopecia and nausea, vomiting or diarrhea not receiving adequate treatment

^b An interruption of tazemetostat for more than 14 days due to any toxicity must be discussed with the Medical Monitor before treatment can be resumed

^c Excluding Grade 2 and 3 anemia: subjects are allowed to continue tazemetostat at their current dose level with transfusion per Investigator discretion

^d Excluding Grade 2 neutropenia and thrombocytopenia

^e Use of growth factors (G-CSF, GM-CSF) is permitted as per ASCO or institutional guidelines

f Subjects are allowed to receive platelet transfusion per Investigator discretion

post-progression if they meet the 2014 Lugano Classification (Cheson, 2014; Appendix 3) criteria for disease progression as well as the following criteria:

- absence of symptoms and signs (including worsening of laboratory values, eg, new or worsening hypercalcemia) that indicate unequivocal disease progression
- no decline in ECOG performance status
- absence of tumor growth at critical anatomical sites (eg, leptomeningeal disease) that cannot be managed by protocol-allowed medical interventions

Subjects whose radiographic disease progression is confirmed at a subsequent tumor assessment may be considered for continued study treatment at the discretion of the Investigator if they have evidence of clinical benefit and continue to meet the above criteria. Investigators who note subjects with disease progression that are receiving continued clinical benefit without clinical deterioration must contact the Medical Monitor to discuss the assessment of risk/benefit of maintaining the subject on study.

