- Tumor response assessments by disease-appropriate standard criteria (2014 Lugano Classification [Appendix 3]) using ¹⁸FDG-PET and CT, or combined as PET-CT, of known sites or newly suspected sites of disease (neck, chest, abdomen, and pelvis required at all time points). MRI instead of CT if clinically indicated. Additional imaging of brain or bone by MRI or CT if clinically indicated at screening and during the study for CNS signs/symptoms or bone marrow involvement. Radiologic tumor assessments will be performed at screening between day -28 and day -1 and at specified time points (±7 days) during study treatment beginning from start of treatment (C1D1), irrespective of treatment delays, until loss of clinical benefit or disease progression (i.e., C3D1, C6D1, C12D1, C18D1, C24D1, etc). CT imaging (as PET-CT or CT alone) must include diagnostic quality CT scan AND should preferably be contrast enhanced; FDG-avid disease should report PET-CT based response, non FDG-avid disease should report CT based response. Tumor assessment at EOT required if no disease progression previously documented. Subjects who discontinue study treatment for any reason other than disease progression will continue to undergo tumor response assessments at timepoints (±7 days) as scheduled until disease progression. A standard-of-care clinical examination for lymphoma, including assessment of B symptoms, will be performed at screening and with tumor assessments (See Section 11).
- ^m CT of neck, chest, abdomen, and pelvis required at screening then during study treatment (±7 days) at C3D1, C6D1, C12D1, C18D1, and C24D1, as well as EOT. If no disease progression previously documented and subject continues treatment with tazemetostat beyond 24 cycles, CT will be required every 6 months (±7 days) at C30D1, C36D1, etc. During Survival Follow-up, CT performed every 6 months (±30 days) for 2 years then every 12 months (±30 days) thereafter, or until disease progression (See Section 11).

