8.1. Study Population

8.1.1. Inclusion Criteria

- 1. Men and women of 18 years of age and older
- 2. Voluntary agreement to provide written informed consent and the willingness and ability to comply with all aspects of the protocol
- 3. Eastern Cooperative Oncology Group (ECOG) score of 0, 1, or 2 (Appendix 1)
- 4. Life expectancy (in the opinion of the Investigator) of ≥ 3 months before enrollment
- 5. Have histologically confirmed FL, Grade 1 to 3a. Subjects may have R/Rdisease following at least 2 standard prior systemic treatment regimens where at least 1 anti-CD20-based regimen was used
- 6. Treatment recommended in accordance with the Groupe d'Etude des Lymphomes Folliculaires (GELF) criteria due to the presence of at least one of the following:
 - a. Any nodal or extranodal tumor mass >7 cm diameter
 - b. Involvement of at least 3 nodal sites, each with diameter >3 cm
 - c. Presence of any systemic or B symptoms
 - d. Splenic enlargement with inferior margin below the umbilical line
 - e. Compression syndrome (ureteral, orbital, gastrointestinal)
 - f. Pleural or peritoneal serous effusion (irrespective of cell content)
 - g. Leukemic phase (>5.0 x 10⁹/L circulating malignant cells)
 - h. Cytopenias (granulocyte count $\leq 1.0 \times 10^9/L$ and/or platelets $\leq 100 \times 10^9/L$)
- 7. Meet the following laboratory parameters:
 - a. Absolute neutrophil count (ANC) \geq 750 cells/ μ L (0.75 x 10⁹/L), or \geq 500 cells/ μ L (0.50 x 10⁹/L) in subjects with documented bone marrow involvement
 - b. Platelet count $\geq 50,\!000$ cells/µL (50 x 109/L), or $\geq 30,\!000$ cells/µL (30 x 109/L) in subjects with documented bone marrow involvement, and without transfusion dependence
 - c. Hemoglobin $\geq 8 \text{ g/dL}$
 - d. Serum alanine aminotransferase (AST) and aspartate aminotransferase (ALT) \leq 3.0 x ULN, unless related to disease involvement
 - e. Total bilirubin ≤ 1.5 x ULN, unless due to disease involvement, Gilbert's syndrome, or hemolytic anemia

- f. Estimated creatinine clearance (ie, estimated glomerular filtration rate [eGFR] using Cockcroft-Gault [Appendix 4]) ≥ 40 mL/min
- 8. At least one bi-dimensionally measurable nodal lesion > 1.5 cm in its longest diameter by computed tomography (CT) scan or magnetic resonance imaging (MRI) excluding lesions that meet the following criteria:
 - a. Previously irradiated lesions should not be counted as target lesions

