12.1.6. Laboratory Assessments

Clinical laboratory samples will be collected at the visits designated in the Schedule of Visits and Procedures (Table 2). The clinical laboratory parameters that will be measured are detailed in Table 7.

All routine, scheduled clinical laboratory assessments and screening laboratory assessments (see below) will be conducted locally only (these samples should not be sent to central laboratory for testing unless local testing is not available):

- Hematology
- Comprehensive chemistry panel
- Lactate dehydrogenase(LDH)
- Peripheral blood smear (Section 12.1.8)

- Cytogenetic testing and, if necessary, DNA sequencing by NGS of bone marrow aspirate/biopsy for subjects with abnormal morphology in peripheral blood smear suggestive of MDS/AML or MPN (performed by local laboratory, please refer to Lab Manual for details. Please see below if local laboratory is not equipped.)
- Viral serology/virology (Section 12.1.7)
- Pregnancy testing (serum or urine as indicated) (Section 12.1.9)
- The below samples/assessments may be conducted at the appropriate central laboratory:
 - If local laboratory is unable to perform cytogenetic testing and, if necessary, DNA sequencing of prespecified disease-related genes by NGS, or if results are inconclusive/indeterminate: bone marrow aspirate/biopsy for subjects with abnormal morphology in peripheral blood smear suggestive of MDS/AML or MPN can be sent to central laboratory for testing as backup.

NOTE: In the future, any of the blood and tissue samples that were not completely used may be used for additional research.

A Laboratory Manual will be provided to detail handling, processing, and shipping procedures.

All hematology and serum chemistry (including pregnancy testing, where applicable) samples are to be obtained before study drug administration and results reviewed before administration/dispensing of study drugs. For the management of clinically significant laboratory abnormalities, refer to the dose adjustment criteria for tazemetostat in Section 7.4.1.

A laboratory abnormality may meet the criteria of an AE as described in this protocol (Section 12.2.1.1) and the eCRF completion guidelines. In these instances, the AE corresponding to the laboratory abnormality will be recorded on the Adverse Event eCRF.

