13. BIOMARKER ASSESSMENTS

14. STATISTICS

This section is a summary of the planned statistical analyses of the most important endpoints including primary and key secondary endpoints. A statistical analysis plan (SAP) will be finalized prior to final database lock. Should the SAP and the protocol be inconsistent with respect to any further planned analyses, the language of the SAP is governing.

All statistical analyses will be performed by the Sponsor or designee. Sample and power calculations are based on nQuery 8.0.

Definitions of Analysis Sets

The analysis sets will be defined as follows:

- Futility Analysis Set will comprise of the first 15 subjects regardless of EZH2 status who received at least 1 dose of study drug and had tumor assessment at both baseline and Cycle 6.
- **Primary Analysis Set** will comprise of the first 43 subjects regardless of EZH2 status who received at least 1 dose of study drug and had tumor assessment at both baseline and at least one post-baseline timepoint (Cycle 3, Cycle 6, Cycle 12, Cycle 18, and Cycle 24).
- Full Analysis Set (FAS) will include all subjects who received at least 1 dose of study drug and had tumor assessment at baseline and at least one post-baseline timepoint (Cycle 3, Cycle 6, Cycle 12, Cycle 18, and Cycle 24). This will be the overall analysis set for efficacy evaluations.
- Safety Population will include all subjects who received at least 1 dose of the study drug and have at least 1 post-baseline safety evaluation, regardless of mutation status. This will be the analysis set for all safety evaluations.

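### From Cycle 2 the retreatment counts are stricter than the entry counts allowed with marrow involvement, so unchanged counts alone force a tazemetostat hold

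*Protocol*

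**What the plan says.** All counts are × 10⁹/L.

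- **Entry (Protocol 8.1.1, criteria 7a and 7b; same in the synopsis).** The general floors are ANC 0.75 and platelets 50. Lower floors, ANC 0.50 and platelets 30, apply to one group. For platelets the clause reads "in subjects with documented bone marrow involvement, and without transfusion dependence".
- **Continuation (Protocol 7.4.1).** "For continuation of treatment for Cycle 2 and beyond, subjects must meet the following retreatment criteria": platelets above 50, ANC at least 0.75, and Grade 3 or higher toxicity resolved. Only the toxicity criterion accepts a return to baseline.
- **Restart after drug-related toxicity (Table 1).** After Grade 3 thrombocytopenia, tazemetostat may restart once the event has "resolved to Grade ≤ 2 or baseline". After an ANC below 0.75, it may restart only at 0.75 or more, with no baseline option.
- **When the rule bites (Protocol 12.1.6).** Hematology and chemistry "samples are to be obtained before study drug administration and results reviewed before administration/dispensing of study drugs".
- **Amendment summary, Section 7.4 entry.** The reason given for changing the tazemetostat dose modifications begins "To align with the inclusion criteria and retreatment".

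The SAP does not address the point.

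**The concern.** The protocol lets a subject start at counts that its own continuation rule does not accept one cycle later. Low counts in this group may reflect disease in the marrow rather than the drug, and the entry criteria make an explicit allowance for that. The continuation criteria drop the allowance.

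An eligible subject without toxicity then has two routes at Cycle 2: a tazemetostat hold until counts rise, or support with growth factor or platelet transfusion to pass the check. Table 1 adds a second difficulty. For some subjects it permits a restart that the continuation criteria forbid, so two sites could handle the same subject differently. What is at stake is who is dosed and whether sites act consistently.

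**Working it through.** No sample size, power or error rate is involved. The check is a comparison of thresholds.

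**1. Entry against continuation**

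| | Entry, marrow involved (7a, 7b) | Entry, others (7a, 7b) | Cycle 2 onward, all subjects (7.4.1) | Gap for marrow-involved subjects |
|---|---|---|---|---|
| ANC | ≥ 0.50 | ≥ 0.75 | ≥ 0.75 | 0.75 − 0.50 = 0.25 |
| Platelets | ≥ 30 | ≥ 50 | > 50 | 50 − 30 = 20 |

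For subjects without marrow involvement the limits agree, except at a platelet count of exactly 50. For marrow-involved subjects the affected entry ranges are ANC 0.50 to below 0.75 and platelets 30 to 50.

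**2. Worked case.** Marrow-involved subject, ANC 0.60 and platelets 40, unchanged at Cycle 2 Day 1.
- Entry: 0.60 ≥ 0.50 and 40 ≥ 30, so 7a and the 7b count floor are met.
- Cycle 2: 0.60 < 0.75 and 40 is not above 50, so both count criteria fail.
- The toxicity criterion is not in play, because nothing has changed.

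**3. Does exclusion 6 remove these subjects?** As printed it excludes cytopenias above Grade 3. Table 1 gives Grade 3 neutropenia as ANC below 1.0 down to 0.5, so an entry ANC of 0.50 to 0.74 is Grade 3 and stays eligible. If the sign were meant to include Grade 3, exclusion 6 would itself contradict 7a.

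**4. Does Table 1 relax the criteria?** No. It covers tazemetostat-related toxicity only. Within that scope it adds two problems:
- Platelets, baseline 40, with a drug-related Grade 3 fall that recovers to 40: Table 1 permits restart, but the continuation criterion (above 50) forbids the next cycle.
- ANC, baseline 0.60, with a drug-related fall to 0.52: Table 1 requires 0.75 to restart, which is above the subject's own entry value.

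**5. How often the check recurs.** Table 2 schedules Day 1 hematology after Cycle 1 at Cycles 2 to 6 (5 visits) and at Cycles 9, 12, 15, 18, 21 and 24 (6 visits): 5 + 6 = 11. This counts occasions on which the rule applies; it is not an effect size.

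**6. What a hold does not do.** Interruptions are allowed; one longer than 14 days needs discussion with the Medical Monitor before resuming (7.4.1). Scans continue "irrespective of treatment delays, until loss of clinical benefit or disease progression". The Primary Analysis Set takes subjects who "had tumor assessment at both baseline and at least one post-baseline timepoint", and the Full Analysis Set has the same requirement. So a hold neither ends treatment nor makes a subject a non-responder, and a subject with no post-baseline scan is outside both sets.

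**The case against.** **A deliberate safety floor.** Permission to start at low, disease-driven counts need not extend to 24 cycles at those counts. Section 5.2.2 lists thrombocytopenia (5%) and neutropenia (3%) as the leading causes of tazemetostat interruption, and the 0.75 limit appears in both the criteria and Table 1. The amendment entry does not say which entry floor was meant. This is a possible reading, but a weak one. The limits 0.75 and 50 reproduce the general entry floors with only the marrow clause missing, and no section gives a reason for being stricter at Cycle 2 than at Cycle 1. The baseline option for platelets in Table 1 also matters only when baseline is worse than Grade 2. Taking that to mean below 50 (an assumption, since Table 1 prints no platelet bands), requiring both rules together leaves the option with no use. The amendment entry is only a hint of intent and carries no weight beyond that.

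**Sites have one answer.** For unchanged counts this is right: the criteria are mandatory, so the result is a hold. The risk of inconsistency is confined to the Table 1 overlap.

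**Support is permitted.** Growth factor is allowed, and Table 1 footnote f states: "Subjects are allowed to receive platelet transfusion per Investigator discretion". Criterion 7b governs entry only, so transfusion on study breaches nothing. This stands, but it means treating a count in order to satisfy a rule that the subject did not have to meet at entry.

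**Little is at stake.** The number of affected subjects is unknown and the trial has ended. Both points stand and limit the weight of the finding.

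**Conclusion.** The concern holds. As printed, a marrow-involved subject who enters with ANC 0.50 to below 0.75, or platelets 30 to 50, and does not change fails the Cycle 2 continuation rule without any drug toxicity. Section 7.4.1 does not use the word hold; it follows from the criteria being mandatory. Table 1 dose reductions do not follow, because they require drug-related toxicity.

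The conclusion rests on the inequality signs as printed. If the platelet limit were meant to include 50, only a count of exactly 50 would change.

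The group is foreseeable. Inclusion 6h makes cytopenia a qualifying reason for treatment, and Section 5.1 puts marrow involvement at 70% of patients with follicular lymphoma. That 70% is not the share below the floors, which the documents do not give. No effect on response rate or power is therefore claimed. SAP 5.2 reports early termination with 5 treated patients, and SAP 9 plans no efficacy analysis. The point is worth correcting as an inconsistency in dosing rules.

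**What to change.** Preferred: in Section 7.4.1, add a return-to-baseline alternative, limited to subjects with documented marrow involvement, to the platelet and ANC continuation criteria, and add the same alternative to the ANC below 0.75 row of Table 1. The cost is protocol wording, plus continued dosing of some subjects at the low counts at which they are already allowed to start. Two limits remain. A subject slightly under baseline (38 from 40, say) would still fail, and the Grade 4 row of Table 1 would still have no baseline option, although dosing after a Grade 4 event already goes to the Medical Monitor.

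Alternative, if the sponsor judges dosing at these counts unsafe: delete the lower floors (ANC 0.50, platelets 30) from 7a and 7b in the synopsis and Section 8.1.1. The cost is that fewer marrow-involved subjects would be eligible.

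Either change makes the entry and continuation rules consistent.

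### After a Grade 4 non-hematologic toxicity, Table 1 lets the tazemetostat interruption end at Grade 2, one grade looser than after a Grade 2 event or a first or second Grade 3 event

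*Protocol*

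**What the plan says.** Protocol Section 7.4.1 governs interruption and restart of tazemetostat for related toxicity, in text and in Table 1.

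- **General restart rule (text):** "the treatment may restart once the toxicity has been resolved to Grade ≤ 1 or baseline, unless otherwise noted".
- **Retreatment criterion for Cycle 2 onward (text):** "Any Grade 3 or higher toxicity must have resolved to ≤Grade 1 or baseline, unless otherwise noted".
- **Table 1, Grade 2:** interrupt until "resolved to Grade ≤ 1 or baseline". One cell covers the first to fourth occurrences.
- **Table 1, general Grade 3 block, labelled** "Not Including Neutropenia and Thrombocytopenia": the same recovery level for the first and second occurrences. The third occurrence reads "Discontinue tazemetostat".
- **Table 1, Grade 3 thrombocytopenia:** interrupt until "resolved to Grade ≤ 2 or baseline". Grade 3 neutropenia has its own ANC threshold.
- **Table 1, Grade 4, any occurrence:** "Interrupt tazemetostat until resolved to Grade 2 or less", with "Discuss with Medical Monitor" in the dose column. This row is not divided into hematologic and non-hematologic toxicity.

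The table footnotes remove alopecia and inadequately treated nausea, vomiting or diarrhea (a), Grade 2 and 3 anemia (c), and Grade 2 neutropenia and thrombocytopenia (d).

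**The concern.** A recovery threshold would normally be at least as strict after a worse event. Here the order is reversed for non-hematologic toxicity. Section 12.3.1 defines Grade 4 as life-threatening, yet such an event meets its written recovery level at Grade 2. A toxicity that never went beyond Grade 2 has to fall further before dosing resumes.

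It is also unclear which instruction applies to a Grade 4 event that has improved to Grade 2. The Grade 2 rows would themselves call for interruption. The Cycle 2 retreatment criterion would block dosing, unless the Grade 4 row counts as one of the exceptions it allows. Sites could reasonably act differently. On one reading, a subject who has had a life-threatening drug-related event is put forward for restart at a level where dosing would otherwise be withheld.

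**Working it through.** The plan states no figure on this point, so the main check is a comparison of the rows.

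**Step 1. Recovery level by worst grade, for in-scope non-hematologic toxicity**

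| Event | Recovery level | Next step |
|---|---|---|
| Grade 2, 1st | Grade ≤1 or baseline | Same dose |
| Grade 2, 2nd and 3rd | Grade ≤1 or baseline | 600 mg, then 400 mg BID |
| Grade 2, 4th | Grade ≤1 or baseline | Medical Monitor |
| Grade 3, 1st and 2nd | Grade ≤1 or baseline | 600 mg, then 400 mg BID |
| Grade 3, 3rd | None | Stop permanently |
| Grade 4, any | Grade ≤2 | Medical Monitor |

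The Grade 4 level is one grade looser than the Grade 2 and Grade 3 levels whenever baseline is Grade 0 or 1. If the toxicity was already Grade 2 at baseline, the levels coincide. Inclusion criterion 9 makes that possible, because it admits prior-treatment toxicity above Grade 1 if stable and not clinically significant.

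**Step 2. Does the text override the row?** Not clearly. Both general rules ask for Grade ≤1 or baseline, but both allow exceptions noted elsewhere. The Grade 4 row can be read as such an exception. This is an ambiguity between text and table, not a flat contradiction. The reversal itself lies within Table 1.

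**Step 3. Does a hematologic rationale cover it?** Only in part. A Grade ≤2 level matches the thrombocytopenia row, and Section 12.2.4.1.1 names cytopenias as the Grade 3 or 4 identified risks. The table separates neutropenia and thrombocytopenia from other toxicity at Grade 3 but not at Grade 4, so the looser level also reaches non-hematologic events.

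**Step 4. Size.** The documents give neither of the two quantities needed, so both are assumed:
- p = proportion of subjects with an in-scope related non-hematologic Grade 4 event: 1% to 5%.
- f = share of those restarted while still at Grade 2: 10% to 100%. The value 100% gives an upper bound.

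Expected number = n × p × f. Chance of at least one = 1 − (1 − p × f)^n.

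| n | f | p = 1% | p = 5% |
|---|---|---|---|
| 59 planned | 100% | 0.59 (chance 0.447) | 2.95 (0.952) |
| 59 planned | 50% | 0.295 (0.256) | 1.475 (0.775) |
| 59 planned | 10% | 0.059 (0.057) | 0.295 (0.256) |
| 5 treated | 100% | 0.05 (0.049) | 0.25 (0.226) |
| 5 treated | 10% | 0.005 (0.005) | 0.025 (0.025) |

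For example, 59 × 0.05 × 1 = 2.95, and 1 − 0.95^59 = 0.952.

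**The case against.** The strongest reply is that the Grade 4 row, read across both columns, is the more restrictive one. After a first Grade 3 event a site may restart at 600 mg BID without mandatory consultation, unless the interruption exceeds 14 days. After Grade 4 no restart dose is authorised and every occurrence goes to the Medical Monitor, so reaching Grade 2 opens a discussion and does not trigger a restart. A site that applied every row and the retreatment criterion together would not dose at Grade 2 at all. Other safeguards exist: Grade 4 events are serious by definition (12.3.1) and reach the Sponsor within one business day (12.4), the Investigator may stop treatment at any time (8.2.1), and Section 14.7 sets stopping boundaries that cover Grade >3 non-hematologic events.

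Much of this stands, and it is why the point is minor. It does not explain the looser level. The fourth Grade 2 occurrence also goes to the Medical Monitor, yet keeps the stricter threshold, so the table already combines the two. None of the other safeguards sets the recovery level for an individual restart, and the reading that blocks dosing is only one of those the text permits.

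The size estimate is also open to challenge. Section 5.2.2 lists the most common adverse events leading to interruption in adults as thrombocytopenia (5%), neutropenia (3%), and anemia and diarrhea (2% each). Those leading to dose reduction were each under 1%. These figures are per term and not restricted to Grade 4, so they do not rule out a 5% total. They do make the upper end of the assumed range look high, and 2.95 of 59 should carry little weight.

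**Conclusion.** The concern holds, as a minor point. For tazemetostat-related non-hematologic toxicity within Table 1, and a baseline of Grade 0 or 1, the written recovery level is one grade looser after Grade 4 than after Grade 2 or a first or second Grade 3 event. The protocol gives no reason for this, and its text does not say which rule prevails. This rests on the wording alone.

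How many subjects would actually restart at Grade 2 cannot be estimated from the documents. The figures above are illustrations under assumed rates. SAP Section 5.2 records that the study stopped early with 5 treated patients, so the consequence for this trial is close to nil.

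**What to change.** Split the Grade 4 row of Table 1 in two:

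- **Non-hematologic Grade 4:** interrupt until Grade ≤1 or baseline before any restart is considered.
- **Hematologic Grade 4:** keep the present Grade 2 or less.

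Keep the Medical Monitor discussion for both. The split removes the reversal and, for non-hematologic events, the conflict with the retreatment criterion. It leaves open whether the retained hematologic level is an exception to that criterion. A clause in the criterion naming the hematologic rows of Table 1 as the exceptions would settle that too.

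The cost is one table row and, if wanted, one clause. The clinical downside is a somewhat longer interruption for a few subjects.
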